## **3.2. Sample Size Justification**

The planned sample size for the study is 972 randomized participants (324 for each of the three study groups). The binomial regression analysis described for the binary outcomes of Specific Aim 1 drive this sample size calculation because binary outcomes contain the least amount of information (and hence, yield the lowest statistical power). The assumptions that lead to this sample size of 972 randomized participants are as follows:

1. binomial regression with the proportion of occurrences out of four time points
2. 90% statistical power
3. two-sided, 0.025 significance level test (Bonferroni correction) comparing RLP to control, RLP+ to control, and RLP to RLP+ within each stratum
4. effect size of 0.10 (difference between rates of 0.25 and 0.35)
5. 10% lost to follow-up per year, 10% lost per year for women who change their minds about intending pregnancy, and another 10% lost per year for those women who become pregnant (intentionally or unintentionally)

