### 11.3. Analytic Methods

#### 11.3.1. Specific Aim 1

The outcome variables are binary (contraception use; satisfied with contraceptive method) and ordinal (contraceptive method effectiveness), and will be measured at four time periods post-baseline (6, 12, 18, and 24 months). For the binary outcome variables, we will construct a proportion for each participant as the number of time periods in which the participant's response is positive, divided by the number of time periods in which the participant is not intending pregnancy. The denominator will be four, except for those participants who withdraw consent from the study, change their minds about intending pregnancy during the study, or become pregnant. Therefore, we will apply a binomial regression analysis to these proportions. We will use intervention group assignment (intention-to-treat analysis) as the sole regressor in the primary analysis, but we will investigate in secondary analyses the effects of selected covariates on the proportional response (demographics; pregnancy history; sexual and contraceptive history; perceived control/fatalism toward contraception; relationships; compliance with log-in requirements). In terms of the three randomized groups, we will construct two-sided test statistics for comparing: 1) RLP to control, 2) RLP+ to control, and 3) RLP to RLP+. Therefore, we will impose a Bonferroni correction factor to the significance level ( $\alpha = 0.0167$ ). We will apply additional secondary analyses that are longitudinal, in which we invoke a logistic regression model with random participant effects to investigate if there are any time period effects and/or time period by intervention interactions for the binary outcomes. Finally, we will invoke a shared parameter model to account for the informative censoring that could occur due to participant withdrawal in a longitudinal study. In our setting, the shared parameter model includes a Weibull time-to-event regression model for the time to participant withdrawal in conjunction with a logistic regression model with random participant effects for the binary outcome.

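### The primary binomial regression has no allowance for correlation among a woman's repeated answers, so its type I error would exceed 0.0167 by an amount that depends on a within-woman correlation the protocol does not give

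*Protocol*

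**What the plan says.** Section 11.3.1 of the protocol defines the primary analysis. Each woman's yes/no answers at 6, 12, 18 and 24 months become one proportion: periods with a positive response over periods in which she is not intending pregnancy. On the denominator it says "The denominator will be four, except for those participants who withdraw consent from the study"; a change of pregnancy intention or a pregnancy also reduces it. The model follows: "Therefore, we will apply a binomial regression analysis to these proportions". On its content: "We will use intervention group assignment (intention-to-treat analysis) as the sole regressor in the primary analysis". Three pairwise two-sided comparisons are each tested at 0.0167.

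Within-woman dependence enters only after the primary analysis: "We will apply additional secondary analyses that are longitudinal, in which we invoke a logistic regression model with random participant effects". A shared parameter model with random participant effects is also listed.

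Section 3.2 bases the sample size on "binomial regression with the proportion of occurrences out of four time points", with "90% statistical power", a two-sided level of 0.025, rates of 0.25 and 0.35, and three sources of loss of 10% per year each. The result is 324 per arm, 972 in all. No within-woman correlation is among the listed assumptions.

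**The concern.** A binomial count out of k has variance k·p(1−p) only if the k answers are independent given the model. With group as the sole regressor, all women in an arm share one p, so lasting differences between women go unmodelled. Such differences are to be expected. The effectiveness table in 11.2.2.1 includes sterilization, IUDs and implants, which carry over from one assessment to the next. The typology in 11.2.3.1 has categories for continuous users of one method and for continuous nonusers.

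If answers within a woman are positively correlated, the model-based standard error is too small, the confidence intervals are too narrow, and the three primary tests reject too often. The Bonferroni step, meant to hold the overall error near 0.05, would not do so. The power in 3.2 would also be lower than under independence.

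**Working it through.** **Inputs.** From 3.2: rates 0.25 and 0.35, two-sided 0.025, power 90%, 324 per arm, loss 3 × 10% = 30% per year. From 11.3.1: up to m = 4 answers per woman, nominal 0.0167 per comparison. The ICC is not in the protocol; 0.1 to 0.5 is an assumed range.

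**Step 1: the plan's own figure.** Observations per arm for two proportions, pooled variance, no continuity correction:

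n = [2.2414·√(2·0.30·0.70) + 1.2816·√(0.25·0.75 + 0.35·0.65)]² / 0.10² = 519.0

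Divide by 4 answers per woman counted as independent, and by retention 1 − 2 × 0.30 = 0.40:

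519.0 / 4 / 0.40 = 324.4, against 324 stated.

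Conversely, 324 × 0.40 × 4 = 518.4 independent observations give power 0.900. One observation per woman would need 519.0 / 0.40 ≈ 1,298 per arm. Retention of 0.7² = 0.49 would give 265.

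**Step 2: two readings of loss.**
- *Flat 60% loss* (the reading that recovers 324): 40% of women give all four answers and the rest give none. Design effect DE = 1 + 3·ICC on 518.4 observations per arm.
- *Staggered loss* (30% per year, with women contributing until lost): proportions present are 0.837, 0.700, 0.586 and 0.490, a mean of 2.61 answers per woman, or 846 observations per arm. The weighted cluster size is E[k²]/E[k] = 9.295 / 2.612 = 3.56, so DE = 1 + 2.56·ICC.

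**Step 3: actual type I error of the plain binomial test at nominal 0.0167.** Error = 2·[1 − Φ(2.393/√DE)].

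| ICC | DE, four answers | Error | DE, staggered | Error |
|---|---|---|---|---|
| 0.1 | 1.30 | 0.036 | 1.26 | 0.033 |
| 0.2 | 1.60 | 0.058 | 1.51 | 0.052 |
| 0.3 | 1.90 | 0.082 | 1.77 | 0.072 |
| 0.5 | 2.50 | 0.130 | 2.28 | 0.113 |

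With four answers the error doubles at an ICC of about 0.09 and triples at about 0.16.

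A beta-binomial simulation (324 per arm, 10,000 trials per setting, rates 0.3 and 0.9) agrees. At ICC 0.2 / 0.3 / 0.5 it gives 0.057 / 0.082 / 0.126–0.131 with four answers and 0.050–0.053 / 0.068–0.071 / 0.118–0.119 with attrition. A woman-level robust variance brings it back to 0.015–0.019. The chance of at least one false positive over the three comparisons is about 0.13–0.14, 0.16–0.19 and 0.26–0.29 at those ICCs, against a nominal 0.05.

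**Step 4: power with a valid variance at 0.025, the level in 3.2.** Divide the observations per arm by DE and recompute.

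| ICC | Flat 60% loss | Staggered loss |
|---|---|---|
| 0 | 0.90 | 0.99 |
| 0.1 | 0.80 | 0.96 |
| 0.2 | 0.71 | 0.92 |
| 0.3 | 0.62 | 0.87 |
| 0.5 | 0.49 | 0.77 |

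**The case against.** The strongest reply is that 11.3.1 names a model family and a regressor but no variance estimator. A quasi-binomial or sandwich-variance fit is also a binomial regression of per-woman proportions, and such detail is often left to an analysis plan, which is not shown here. This has some force. But the protocol does place participant effects, and only in the secondary models. Its sample size also matches a calculation with independent answers to within one woman. The text as it stands therefore points to the plain variance, and nothing in it points to another.

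A reader might go further and infer that the type I error is several times 0.0167 as a fact, or that the sample size proves an ICC of zero. The documents support neither. No ICC is given, and at 0.1 the inflation is about twofold. The match to 324 requires lost women to contribute nothing, whereas 11.3.1 keeps partial contributors with smaller denominators. Under staggered loss, 324 per arm has power 0.92 at ICC 0.2 and 0.89 at 0.26, so 90% would also fit a correlation of about 0.25. The protocol cannot settle which was meant.

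Two further cautions stand. Power computed at 0.0167 should not be set against the 90% claim, which is made at 0.025; that difference between 3.2 and 11.3.1 is a separate matter. And because the tests are two-sided, about half of the false rejections would favour the comparator.

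The secondary random-effects and shared parameter models would probably expose a primary result produced only by overdispersion. That lessens the problem, but they do not replace the prespecified primary p-value.

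**Conclusion.** The point holds in conditional form. As written, the primary test relies on a variance that is valid only if a woman's answers are independent, and positive correlation makes its type I error exceed 0.0167. The error is about twice nominal at ICC 0.1, about three times or more at 0.2, and 0.11–0.13 at 0.5. That the correlation is positive is a judgement from the nature of the outcome; its size is assumed.

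The 90% power is not assured once the variance is valid. How far it falls depends as much on how loss was handled as on the correlation: under flat 60% loss it falls below 90% at any positive ICC, and under staggered loss only above about 0.25. The primary test should be corrected before it is used.

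**What to change.** In 11.3.1, keep the per-woman proportion, the single regressor and the three comparisons, and name the variance: either a woman-level robust variance (for example logistic GEE clustered on woman) or a quasi-binomial or beta-binomial model.

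In 3.2, state the assumed within-woman correlation and whether lost women contribute their earlier assessments. Restate the power over a range of correlations at the significance level that the analysis will actually use.

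No data collection changes, and no added enrolment is asked for. The cost is a stated power that is likely to be less favourable than 90% over part of the range.

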##### 3.1.1. Primary Hypothesis and Primary Outcome

Compared with random assignment to an information only control group, random assignment to a reproductive life planning tool (RLP) or a reproductive life planning tool plus a contraceptive action planning tool (RLP+) will increase contraceptive use and adherence. The primary outcome variable is contraceptive use when not intending pregnancy, defined as whether the participant is using any contraceptive method to prevent pregnancy (e.g., hormonal methods, barrier methods, withdrawal, natural family planning, etc.).

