## 11. Statistical Consideration

### 11.1. Introduction and Aims

MyNewOptions is a randomized controlled trial designed to test interventions for assisting privately insured women to formulate and achieve their reproductive goals and avoid unintended pregnancy.

- **The primary aim** is to assess whether women in the RLP and RLP+ intervention groups are more likely to use contraception when not intending pregnancy than women in the control group. Secondary outcomes include effectiveness of contraceptive methods chosen, method satisfaction, and contraceptive self-efficacy.
- **The secondary aim** is to assess whether women in the intervention groups have more continuous contraceptive use and contraceptive adherence over a two-year follow-up period than women in the control group.

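### Single-step Bonferroni over the three pairwise contrasts is valid but less efficient than it need be; a step-down test of the same three holds the 5% family-wise level and brings power per control contrast from about 87% to about 92%

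*Protocol*

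**What the plan says.** The primary hypothesis in Protocol section 3.1.1 is framed against control: "Compared with random assignment to an information only control group, random assignment to a reproductive life planning tool (RLP) or a reproductive life planning tool" with action planning. Section 11.1 words the primary aim the same way, asking whether women in the intervention groups "are more likely to use contraception when not intending pregnancy than women in the control group".

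The analysis in section 11.3.1 covers one more contrast: "we will construct two-sided test statistics for comparing: 1) RLP to control, 2) RLP+ to control, and 3) RLP to RLP"+. It continues "Therefore, we will impose a Bonferroni correction factor to the significance level" and gives 0.0167 as the level. All three tests are two-sided and share that level, with no ordering and no step-down.

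Section 3.2 lists the same three contrasts but sizes the trial with a "two-sided, 0.025 significance level test (Bonferroni correction) comparing RLP to control, RLP+ to control, and RLP to RLP+ within each stratum", at 90% power for rates of 0.25 and 0.35, with 324 women per arm (972 in all).

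**The concern.** Three pairwise equalities among three arms are logically linked: any two of them imply the third. Once one is rejected, at most one of the other two can still be true. Single-step Bonferroni ignores this and holds all three tests at 0.0167 throughout. The power is lost on the two contrasts with control, which are the ones the primary hypothesis is about.

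For example, suppose p = 0.001 for RLP+ versus control and p = 0.03 for RLP versus control. Under 11.3.1, RLP is declared negative. A procedure with the same 5% family-wise guarantee would declare it positive.

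The rule in 11.3.1 also falls short of the power promised in 3.2, because that power was computed at 0.025.

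**Working it through.** **Inputs.** Section 3.2: rates 0.25 and 0.35, 90% power, two-sided 0.025, four time points, losses of 10% + 10% + 10% per year, 324 per arm. Section 11.3.1: 0.0167 per test. Section 6.3.2: 1:1:1 allocation. The 5% family-wise level is inferred from 3 × 0.0167 = 0.05; the protocol does not state it.

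**Step 1: reproduce 972.** The pooled two-proportion formula is n = [z(0.9875)·√(2 × 0.30 × 0.70) + z(0.90)·√(0.25 × 0.75 + 0.35 × 0.65)]² / 0.10².

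- With z-values 2.241 and 1.282 this gives 520 observations per arm.
- 520 / 4 = 130 women; 130 / (1 − 0.60) = 325 per arm; 3 × 325 = 975, against 972 stated.
- This route needs four independent observations per woman and losses added to 60% over two years. Neither is stated.
- At 0.0167 the same route gives 566 observations, 354 per arm and 1,062 in total. So 972 belongs to 0.025, not to the level used in the analysis.

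**Step 2: power of one control contrast on the plan's own signal.** The expected z is 2.241 + 1.282 = 3.523.

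- At 0.0167: Φ(3.523 − 2.394) = Φ(1.129) = 0.87.
- At 0.05: Φ(3.523 − 1.960) = Φ(1.563) = 0.94.

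Step-down power must lie between these two, because a control contrast is tested at 0.0167 or, once another contrast has been rejected, at 0.05.

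**Step 3: step-down keeps 5%.** Of the three equalities, the number that are true can be 3, 1 or 0, never exactly 2.

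- Three true: a false rejection needs the smallest p-value to be at most 0.0167, with probability at most 3 × 0.0167 = 0.05.
- One true: a false rejection needs that one p-value to be at most 0.05, with probability at most 0.05.
- None true: no false rejection is possible.

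This requires only that each p-value is valid.

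**Step 4: size of the gain.** Simulation of 1,000,000 three-arm trials with correlated pairwise z-tests, effective n = 324 × 0.40 × 4 = 518.4 per arm, rates 0.25 / 0.35 / 0.35 for control / RLP / RLP+:

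| Procedure | Per control contrast | Both control contrasts |
|---|---|---|
| Bonferroni, three tests at 0.0167 | 0.871 | 0.788 |
| Holm over the same three | 0.895 | 0.834 |
| Shaffer step-down (0.0167, then 0.05 each) | 0.921 | 0.888 |
| Two control contrasts only, 0.025 each | 0.901 | 0.833 |

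At least one significant control contrast: Bonferroni 0.871 + 0.871 − 0.788 = 0.954; step-down 0.921 + 0.921 − 0.888 = 0.954. Direct simulation gives 0.953 under each.

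**Step 5: error rates in the same simulation.** With all three arms equal, family-wise error is 0.044 under either rule. With RLP effective and RLP+ equal to control, false rejection of RLP+ versus control is 0.017 under Bonferroni and 0.050 under step-down.

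**Step 6: sensitivity.** Within-woman correlation is not given. If it halved the information (259.2 per arm), power per control contrast would be 0.538 under Bonferroni and 0.615 under step-down. The absolute powers move a great deal; the direction of the comparison does not.

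**The case against.** The strongest reply is that nothing here is an error. Bonferroni at 0.05/3 is correctly calculated, conventional and valid, so a reader who inferred that the planned test is wrong or inflates false positives would be mistaken. That stands: the point concerns efficiency only.

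A reader might also infer that RLP versus RLP+ is in the family by mistake, since the primary hypothesis does not name it. The documents do not support this. Section 3.1 sets the three arms against one another, and sections 3.2 and 11.3.1 both list the contrast. It is a design choice.

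A related reply is that testing only the two control contrasts, at 0.025 each, is simpler, agrees with the level in 3.2 and gives 0.901 per contrast. That is a legitimate alternative, but it removes RLP versus RLP+ from equal standing. In the calculation that contrast was reached only after both control contrasts were significant. With RLP effective and RLP+ equal to control, its power then fell from 0.871 to 0.015. Step-down keeps all three contrasts.

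It is also fair to say that the gain for showing both interventions is the most striking figure yet answers a question the protocol does not pose, since section 3.1.1 joins the two tools with an or. About 3 of the 5 points gained per contrast equal the gap between 0.025 and 0.0167 (90% against 87%).

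Finally, the higher false-positive rate for an ineffective intervention is a real cost. It stays within the 5% level, but the sponsor should accept it knowingly.

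**Conclusion.** The point holds as a worthwhile, low-cost improvement, not as a flaw in validity. On the plan's own signal, the rule in 11.3.1 gives about 87% power per control contrast against the 90% in 3.2; step-down gives about 92% with the same 972 women.

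It would go too far to say that the trial is likely to miss a positive primary result for want of this change. When both interventions work at the planned effect, at least one control contrast is significant about 95% of the time under either rule. The rise from 79% to 89% for showing both matters only if both are of interest.

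The absolute powers rest on the variance and loss assumptions implied by 972, which the protocol does not spell out. That step-down never rejects less than Bonferroni does not depend on them.

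**What to change.** In section 11.3.1, replace the flat level with wording such as: *The three pairwise p-values are tested by Shaffer's step-down procedure. The smallest is tested at 0.0167; if it is significant, each of the other two is tested at 0.05. The primary hypothesis is supported for an intervention only by that intervention's own contrast with control.* The last sentence matters because RLP versus RLP+ may be the contrast that opens the second step.

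In section 3.2, state the alpha and power for this procedure, which also removes the disagreement between 0.025 and 0.0167. Because the ordinal outcomes in 11.3.1 and 11.3.2 follow the same analysis, say whether the rule applies to them.

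Settle the rule before unblinded results are seen. The change is a few sentences, with no effect on data collection or sample size. Confidence intervals should be labelled as unadjusted or Bonferroni, since Bonferroni intervals will not match every decision. The false-positive rate of about 0.050 (against 0.017) for an intervention equal to control, when the other works, should be acknowledged.

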For the ordinal outcome variable of contraceptive method, we will code it for each participant as 0 (no method), 1 (less effective method), 2 (more effective method), or 3 (most effective method), and we will construct an average score for each participant across those time periods in which the participant is not intending pregnancy. We will apply a weighted regression analysis to these average scores, in which the weighting factor for a participant is the variance of her estimated average. Then the statistical analysis will proceed in a similar manner to that described above for the binary outcomes, and we will embed an ordinal logistic regression model with random participant effects to investigate if there are time period effects and/or time period by intervention interactions.

[figure not shown]
#### 11.3.2. Specific Aim 2

The outcome variables are ordinal (continuity of contraceptive use; contraceptive adherence), and will be measured at four time periods post-baseline (6, 12, 18, and 24 months). For the contraceptive continuation, we will code it for each participant as 0 (continuous non-use), 1 (non-continuous use with gaps when at risk for pregnancy), 2 (non-continuous use with gaps when not at risk for pregnancy), 3 (continuous use with at least one method switch), or 4 (continuous use of one method). For the contraceptive adherence variable, we will code it for each participant as 0 (none), 1 (low), 2 (medium), or 3 (high). We will analyze these ordinal outcomes in the same manner as described above for the ordinal outcome in Specific Aim 1.

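### The weighted regression for the three ordinal outcomes weights each woman by the variance of her average, where precision weighting needs the inverse

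*Protocol*

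**What the plan says.** Section 11.3.1 of the protocol scores method effectiveness from 0 to 3 and reduces it to one number per woman: "we will construct an average score for each participant across those time periods in which the participant is not intending pregnancy". These averages go into a weighted regression "in which the weighting factor for a participant is the variance of her estimated average". The words inverse and reciprocal do not appear, and no other section corrects the sentence.

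Section 11.3.2 opens with "The outcome variables are ordinal (continuity of contraceptive use; contraceptive adherence), and will be measured at four time periods post-baseline" and closes with "We will analyze these ordinal outcomes in the same manner as described above for the ordinal outcome in Specific Aim 1". The weight therefore also governs continuity (scored 0 to 4) and adherence (scored 0 to 3), which section 11.2.3 lists as the primary outcome variables of Aim 2.

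The number of assessments behind each average differs between women. For the binary outcomes section 11.3.1 says: "The denominator will be four, except for those participants who withdraw consent from the study", and it adds change of intention and pregnancy as further reasons. Section 3.2 plans for "10% lost to follow-up per year, 10% lost per year for women who change their minds about intending pregnancy", plus another 10% per year for pregnancy.

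**The concern.** In weighted least squares a precise observation should count more, so the weight is proportional to one over the variance. Here the weight is the variance, and the least certain averages count most.

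If each woman's own sample variance is meant, the weight depends on what happened to her after randomisation. Only the assessments from 6 to 24 months enter the average, and the intervention starts at baseline. A woman who moves to a most effective method before month 6 and keeps it scores 3, 3, 3, 3 and gets weight zero. On adherence, Table 3 assumes high adherence for sterilisation and long-acting methods, so a woman who stays on one has a constant score by construction. The comparison would rest on women whose score changed during follow-up, which is not the randomised population that the intention-to-treat analysis is meant to describe.

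**Working it through.** The protocol attaches no figure to this weighting, so there is none to reproduce.

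**Inputs from the protocol.** 324 women per arm; three losses of 10% per year, taken together as 30% per year (section 3.2); four post-baseline assessments; effectiveness scored 0 to 3 (section 11.3.1).

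**Assumptions.** Once lost, a woman does not return. Each woman re-chooses a method with probability 5% to 40% per 6 months and may draw the same category again. The control mix of scores 0/1/2/3 is 15/30/40/15%. The true arm difference is a lasting 0.20 points.

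**Step 1, weights under the own-variance reading.** With k assessments and sample variance s², the variance of the average is s²/k.

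- 2,2,2,2 or 0,0,0,0: s² = 0, weight 0
- 2,2,3,3: s² = 1/3, weight 0.333/4 = 0.083
- 0,3,0,3: s² = 9/3 = 3, weight 3/4 = 0.75
- 0,3 (two assessments only): s² = 4.5, weight 4.5/2 = 2.25
- one assessment: s² undefined, no weight

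The most erratic woman with the fewest assessments gets the most weight.

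**Step 2, share without weight, by hand at 10% re-choosing.** Retention per 6 months is √0.7 = 0.837. Among women with at least one assessment, the shares with k = 1, 2, 3, 4 are 0.163, 0.137, 0.114, 0.586. The chance of a constant score is Σp(0.9+0.1p)^(k−1) over the control mix: 0.930, 0.864 and 0.803 for k = 2, 3, 4. Zero variance: 0.137×0.930 + 0.114×0.864 + 0.586×0.803 = 0.70. Adding the 0.16 with one assessment gives 0.86 without weight.

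**Step 3, simulation of method effectiveness** (1,000 runs per column; undefined weights set to zero).

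| Re-choosing per 6 months | 5% | 10% | 20% | 40% |
|---|---|---|---|---|
| Variance exactly zero | 77% | 70% | 58% | 38% |
| One assessment, undefined | 16% | 16% | 16% | 16% |
| No weight in total | 93% | 86% | 74% | 54% |
| Effective sample, share of women analysed | 3.5% | 6.5% | 12% | 21% |
| Mean estimate, own-variance weight (true 0.20) | 0.185 | 0.179 | 0.180 | 0.182 |
| SE, own-variance weight | 0.248 | 0.173 | 0.128 | 0.085 |
| SE, weight k | 0.081 | 0.079 | 0.071 | 0.063 |
| SE, equal weights | 0.078 | 0.073 | 0.068 | 0.064 |
| SE, weight 1/k (common variance) | 0.095 | 0.090 | 0.088 | 0.087 |

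Own-variance against weight k: 0.248/0.081 = 3.1, 0.173/0.079 = 2.2, 0.128/0.071 = 1.8, 0.085/0.063 = 1.35.

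**Step 4, attenuation under other assumptions.** Step 3 has a lasting difference and loses about 10% (0.18 against 0.20). A second simulation (400 runs, mix 10/30/40/20%, 10% re-choosing) moved 20% of intervention women up one category by month 6 and let later re-choosing wash this out. It gave 0.063 with the own-variance weight against 0.127 with weight k, a loss of 1 − 0.063/0.127 = 50%. A repeat gave about 0.05 against 0.13, a loss of 62%. Letting intervention women keep the benefit when they re-choose gave about 0.10 against 0.16, a loss of 38%.

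**Step 5, the common-variance reading.** With variance σ²/k and one σ² for all, the weight is proportional to 1/k. One assessment gets 1, four get 1/4, a ratio of 4 in the wrong direction. The SE relative to weight k is 0.095/0.081 = 1.17, 0.090/0.079 = 1.14, 0.088/0.071 = 1.24, 0.087/0.063 = 1.38. The mean estimate stays between 0.199 and 0.203, so there is no attenuation.

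**The case against.** The wording may be shorthand for inverse-variance weighting, and estimation detail often sits in an analysis plan that is not at hand. That explains how the sentence could arise, but the protocol does not leave the weight open: it fixes it, in the wrong direction. Adding the word inverse would not be enough under the own-variance reading either, because constant women would get infinite weight and women with one assessment would still have none.

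A reader might infer that women on a constant method certainly drop out of all three analyses and that the estimated effect is halved. The documents do not support that, for three reasons:

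- Zero weight follows only if the variance is each woman's own sample variance, which the protocol does not state.
- The condition is a constant score, not a constant method. On adherence, a steady pill user whose medication possession category changes keeps a positive weight. On continuity, gaps can change the score without any change of method.
- Neither switching rates nor the score mix is in the protocol, and only method effectiveness was simulated. The loss of precision appears in every setting tried; the halving belongs to one way of letting the effect act.

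It also stands that the trial's primary outcome is binary and analysed by binomial regression, that the sample size is driven by the binary outcomes, and that an ordinal model with random participant effects is planned alongside, though to examine time effects and their interaction with intervention.

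**Conclusion.** The point holds: the stated weight is the wrong way round under both readings of the variance, for one Aim 1 secondary outcome and both Aim 2 primary outcomes. The direction of the error needs no assumption.

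Its size does. Under the own-variance reading the damage is serious, since most women carry no weight even at 20% re-choosing and about half do at 40%. Under the common-variance reading it is a 14% to 38% larger standard error than with weight k. These figures rest on assumed switching, score mix and effect pattern, and on 30% loss per year without return. They should not be carried over as numbers to continuity or adherence.

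**What to change.** Replace the weighting clause in section 11.3.1 and state that the same rule applies in section 11.3.2. Either of these is sound:

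- Equal weights for the averages, with a robust variance. In the Step 3 runs this was at least as precise as weight k up to 20% re-choosing and about equal at 40%.
- Weights k/(1+(k−1)ρ), where k is the number of contributing assessments and ρ a within-woman correlation pooled over all women, with a robust variance. This is the inverse of σ²(1+(k−1)ρ)/k. It becomes weight k at ρ = 0 and equal weights at ρ = 1, and it is finite and defined for every woman with at least one assessment.

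The cost is one sentence in the protocol, plus the matching line in any analysis plan. It needs no new data and no more participants, and it leaves the binary primary analysis and the sample size unchanged.
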